7. DISCONTINUATION OF STUDY INTERVENTION AND PARTICIPANT DISCONTINUATION/WITHDRAWAL

7.1. Discontinuation of Study Intervention

It may be necessary for a participant to permanently discontinue study intervention. Reasons for permanent discontinuation of study intervention include the following.

- AE (including Grade 3 severity or greater and considered by the investigator to be related to study intervention);
- SAE considered by the investigator to be related to the study intervention;
- Requirement for prohibited concomitant medication;
- Death;
- Pregnancy;
- Study terminated by sponsor;
- Withdrawal by participant or legally authorized representative
- Hospitalization during the active treatment period;
- Miss more than 2 consecutive doses of study intervention.

Note that discontinuation of study intervention does not represent withdrawal from the study. If study intervention is permanently discontinued, the participant will remain in the study to be evaluated for all subsequent scheduled assessments. See the [SoA](#) for data to be collected at the time of discontinuation of study intervention and follow-up for any further evaluations that need to be completed.

In the event of discontinuation of study intervention, it must be documented on the appropriate CRF/in the medical records whether the participant is discontinuing further receipt of study intervention or also from study procedures, posttreatment study follow-up, and/or future collection of additional information.

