10.7. Appendix 7: ECG Findings of Potential Clinical Concern (No Longer Applicable)

10.8. Appendix 8: Prohibited Concomitant Medications That May Result in DDI

PF-07321332 and ritonavir are both primarily metabolized by CYP3A4. Therefore, concomitant use of any medications or substances that are strong inducers of CYP3A4, are prohibited within 28 days prior to dosing of study intervention and during study treatment.

Additionally, ritonavir and PF-07321332 are inhibitors of CYP3A4. Therefore, medications highly dependent on CYP3A4 for clearance and for which elevated plasma concentrations may be associated with serious and/or life-threatening events are not permitted during dosing of PF-07321332/ritonavir (at least 24 hours prior to the first dose of study intervention or as late as Day 1, prior to the first dose of study intervention – see below) and for 4 days after the last dose of PF-07321332/ritonavir. Ritonavir also appears to induce CYP3A, CYP1A2, CYP2C9, CYP2C19, and CYP2B6 as well as other enzymes, including glucuronosyl transferase. Since ritonavir 100 mg q12h is being used to boost the exposure of PF-07321332, no additional DDI is expected other than those associated with ritonavir 100 mg q12h based on in vitro assessments. Thus, the prohibited concomitant medications and those to be used with caution are primarily based on the ritonavir label.

A nonexhaustive list of prohibited and precautionary medications is provided below. If a medication is not listed, it should not automatically be assumed it is safe to co-administer. Appropriately qualified site staff will review all concomitant medications to determine if they are prohibited.

The Pfizer study team is to be notified of any prohibited medications taken during the study. After consulting with the sponsor, the investigator will make a judgement on the ongoing participation of any participant with prohibited medication use during the study.

This list of drugs prohibited for potential DDI concerns with the IMP may be revised during the course of the study with written notification from sponsor, to include or exclude specific drugs or drug categories for various reasons (eg, emerging DDI results for the IMP, availability of new information in literature on the DDI potential of other drugs).

This is not an all-inclusive list. Site staff should consult with the sponsor or designee with any questions regarding potential DDI.

Prohibited Medications that are Strong Inducers of CYP450 3A4^a		

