Due to prolonged induction of CYP450 3A4 participants must not use these medications within 28 days prior to randomization and during dosing of PF-07321332/placebo and ritonavir/placebo.		
Drug Class	Specific Medication	Clinical Comments
Anti-cancer drugs	Apalutamide	Reduced concentrations of PF-07321332/ritonavir; may result in suboptimal concentrations.
Anticonvulsants	Phenytoin, Carbamazepine, Phenobarbital	
Antimycobacterials	Rifampin	
Herbal Products	St. John's Wort	
Prohibited Medications Dependent on CYP450 3A4 for Clearance or with other Notable Interactions^a		
These medications are prohibited for at least 24 hours prior to the first dose of PF-07321332/placebo and ritonavir/placebo, through 4 days after the last dose of PF-07321332/placebo and ritonavir/placebo. If a participant cannot temporarily interrupt the prohibited medication during this period, they should be considered ineligible.		
Drug Class	Specific Medication	Clinical Comments
Alpha 1-Adrenoreceptor Antagonist	Alfuzosin	Risk of hypotension, syncope
Analgesics	Piroxicam, Propoxyphene, Pethidine	Analgesic concentrations may increase.
Antianginal	Ranolazine	Risk of cardiac arrhythmias
Antiarrhythmics	Dronedarone, Amiodarone, Flecainide, Propafenone, Quinidine	Risk of cardiac arrhythmias
Anti-gout	Colchicine	Ritonavir 100 mg twice daily increased colchicine AUC 296% and C _{max} 184%. Potential for serious and/or life-threatening reactions in patients with renal and/or hepatic impairment.
Antipsychotics	Clozapine, Lurasidone, Pimozide	Potential for increased levels of antipsychotics
Ergot Derivatives	Dihydroergotamine, Ergotamine, Methylergonovine	Risk of acute ergot toxicity (peripheral vasospasm and ischemia of the extremities)
Lipid lowering drugs (HMG CoA Reductase Inhibitors)	Lovastatin, Simvastatin	Risk of rhabdomyolysis
PDE-5 Inhibitors for pulmonary arterial hypertension treatment	Sildenafil (Revatio) when used for pulmonary arterial hypertension	Risk of visual disturbances, Co-administration may result in visual abnormalities, hypotension, prolonged erection, and syncope
Sedatives/Hypnotics	oral Midazolam, Triazolam	Risk of prolonged sedation, respiratory depression, or hypnotic concentrations

a. Note: If a drug is not listed, it should not automatically be assumed it is safe to co-administer

Prohibited Medications Dependent on CYP450 3A4 for Clearance or with other Notable Interactions^a		

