These medications are prohibited from the first dose of PF-0321332/placebo and ritonavir/placebo, through 4 days after the last dose of PF-07321332/placebo and ritonavir/placebo. If a participant cannot temporarily interrupt the prohibited medication during this period, they should be considered ineligible.		
Drug Class	Specific Medication	Clinical Comments
Alpha 1-Adrenoreceptor Antagonist	Tamsulosin, Silodosin, Doxazosin (>2 mg daily), Terazosin (>5 mg daily)	Risk of hypotension, syncope
Analgesics	Methadone	Moderate to weak decreases in methadone concentrations have been observed.
Opioid Dependence Treatment	Fentanyl, Oxycodone	Analgesic concentrations may increase.
	Buprenorphine Lofexidine	Co-administration may increase concentrations of Buprenorphine and Lofexidine.
Anticancer drugs	Abemaciclib, Ceritinib, Dasatinib, Encorafenib, Ibrutinib, Ivosidenib, Neratinib, Nilotinib, Venetoclax, Vinblastine, Vincristine	Co-administration contraindicated due to potential loss of virologic response and possible resistance. Avoid co-administration of Encorafenib or Ivosidenib due to potential risk of serious adverse events such as QT interval prolongation. Avoid use of Neratinib, Venetoclax or Ibrutinib. Co-administration of Vincristine and Vinblastine may lead to significant hematologic or gastrointestinal side effects. For further information, refer to individual product label for anticancer drug.
Anticoagulants/ antiplatelet	Rivaroxaban, Warfarin	Possible increased risk of bleeding Possible decreased warfarin effects. Closely monitor INR if co-administration with Warfarin is necessary.

Prohibited Medications Dependent on CYP450 3A4 for Clearance or with other Notable Interactions^a		
These medications are prohibited from the first dose of PF-0321332/placebo and ritonavir/placebo, through 4 days after the last dose of PF-07321332/placebo and ritonavir/placebo. If a participant cannot temporarily interrupt the prohibited medication during this period, they should be considered ineligible.		
Drug Class	Specific Medication	Clinical Comments
Antidepressant	Bupropion	Monitor for an adequate clinical response to Bupropion.
	Trazodone	Adverse reactions of nausea, dizziness, hypotension, and syncope have been observed following co-administration of Trazodone and Ritonavir. A lower dose of Trazodone should be considered. Refer to Trazadone product label for further information.

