Corticosteroids (inhaled or intranasal) (systemic) (Local injections, including intra-articular, epidural, or intra-orbital)	Budesonide, Ciclesonide, Mometasone	Co-administration can increase concentration of Budesonide, Ciclesonide, and Mometasone and can result in adrenal insufficiency and Cushing's syndrome.
	Betamethasone Budesonide	Co-administration can increase concentration of Betamethasone, and Budesonide and can result in adrenal insufficiency and Cushing's syndrome.
	Betamethasone, Methylprednisolone, Prednisone, Triamcinolone	Co-administration can increase Betamethasone, Methylprednisolone, and Triamcinolone concentrations and can result in adrenal insufficiency and Cushing's syndrome.
Endothelin receptor antagonists	Bosentan	Bosentan should be discontinued at least 36 hours prior to the initiation of ritonavir.

Prohibited Medications Dependent on CYP450 3A4 for Clearance or with other Notable Interactions^a		

These medications are prohibited from the first dose of PF-0321332/placebo and ritonavir/placebo, through 4 days after the last dose of PF-07321332/placebo and ritonavir/placebo. If a participant cannot temporarily interrupt the prohibited medication during this period, they should be considered ineligible.
		
Drug Class	Specific Medication	Clinical Comments
Hepatitis C direct acting antivirals (DAAs)	Elbasvir/Grazoprevir, Glecaprevir/Pibrentasvir	
Increased Grazoprevir concentrations can result in ALT elevations.
 
It is not recommended to co-administer Ritonavir with Glecaprevir/Pibrentasvir.

	Ombitasvir/Paritaprevir/Ritonavir and Dasabuvir	Refer to the Ombitasvir/Paritaprevir/Ritonavir and Dasabuvir label for further information.
	Sofosbuvir/Velpatasvir/Voxilaprevir	
Refer to the Sofosbuvir/Velpatasvir/Voxilaprevir product label for further information.
 
Patients on ritonavir-containing HCV regimens should continue their treatment as indicated. Monitor for increased PAXLOVID or HCV drug adverse events with concomitant use.

HIV Antiretrovirals Protease Inhibitors	Lopinavir, Amprenavir, Indinavir, Nelfinavir, Atazanavir, Darunavir, Fosamprenavir, Saquinavir, Tipranavir.	Co-administration may increase HIV protease inhibitor concentrations.

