	Ritonavir or cobicistat containing combination products	
Risk of increased rate of adverse reactions. Appropriate doses of additional Ritonavir in combination with ritonavir-containing combination products with respect to safety and efficacy have not been established.
 
Co-administration will increase Elvitegravir concentrations.

Integrase Inhibitors	Elvitegravir	
Hormonal contraceptive	Ethinyl Estradiol	An additional, non-hormonal method of contraception should be considered.

Prohibited Medications Dependent on CYP450 3A4 for Clearance or with other Notable Interactions^a		
These medications are prohibited from the first dose of PF-0321332/placebo and ritonavir/placebo, through 4 days after the last dose of PF-07321332/placebo and ritonavir/placebo. If a participant cannot temporarily interrupt the prohibited medication during this period, they should be considered ineligible.		
Drug Class	Specific Medication	Clinical Comments
Lipid lowering drugs (HMG-CoA Reductase Inhibitors)	Atorvastatin (>20 mg daily), Rosuvastatin (>10 mg daily) Lomitapide	Risk of rhabdomyolysis Co-administration may increase concentration of lomitapide
Hypoglycemics	Glipizide, Tolbutamide Repaglinide Saxagliptin (>2.5 mg daily)	Potentially decrease Glipizide and Tolbutamide concentrations. Potentially increase Repaglinide concentrations. Co-administration may increase Saxagliptin concentration.
Immunosuppressants	Cyclosporine, Tacrolimus, Sirolimus, Everolimus	Co-administration may increase immunosuppressant concentrations. Therapeutic concentration monitoring is recommended for immunosuppressants.
Long-Acting Beta-Adrenoceptor Agonist	Salmeterol	The combination may result in increased concentrations of Salmeterol and increased risk of cardiovascular adverse events, including QT prolongation, palpitations and sinus tachycardia.
Neuroleptics	Pimozide	Risk of cardiac arrhythmias
Sedatives/ Hypnotics	Midazolam (parenteral), Alprazolam, Bromazepam, Brotizolam, Clonazepam, Cloniprazepam, Delorazepam, Diazepam, Etizolam, Eszopiclone, Halazepam, Lormetazepam, Nitrazepam, Nordiazepam, Quazepam, Suvorexant, Temazepam, Zaleplon, Zolpidem Clorazepate, Estazolam, Flurazepam Zolpidem (>5 mg daily)	Risk of prolonged sedation, respiratory depression, or hypnotic concentrations Co-administration with Ritonavir may increase dose of Clorazepate, Estazolam, and Flurazepam. Co-administration may increase Zolpidem concentration.

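### Appendix 8 gives pimozide two incompatible stop times, contradicts itself on zolpidem at 5 mg or less, and files bosentan's 36-hour stop under a first-dose heading

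*Protocol*

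**What the plan says.** Appendix 8 of the Protocol introduces two start times for drugs cleared by CYP3A4: "at least 24 hours prior to the first dose of study intervention or as late as Day 1, prior to the first dose". The tables that follow apply one or the other. Both lists run until 4 days after the last dose, and both headings add "If a participant cannot temporarily interrupt the prohibited medication during this period, they should be considered ineligible".

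- **Pimozide.** In the 24-hour list, the Antipsychotics row reads "Clozapine, Lurasidone, Pimozide". In the list that begins at the first dose there is a second row: "Neuroleptics Pimozide Risk of cardiac arrhythmias".
- **Zolpidem.** In the first-dose list, the Sedatives/Hypnotics block ends a run of names with "Suvorexant, Temazepam, Zaleplon, Zolpidem", with no dose attached. A later line of the same block lists "Zolpidem (>5 mg daily" (the closing bracket is cut from the quote).
- **Bosentan.** It has one row, in the first-dose list, with the comment "Bosentan should be discontinued at least 36 hours prior to the initiation of ritonavir".

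On timing, the Schedule of Activities (Section 1.3) lets screening, randomization and the first dose fall on one calendar day. Section 4.1 caps screening at 48 hours.

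**The concern.** Appendix 8 is the table that sites use to decide whether a participant on another medicine may be dosed, and when. A drug with two entries and two conditions leaves that decision to whichever entry the staff member finds. Someone who finds pimozide in the Neuroleptics row has no reason to look for it again under Antipsychotics in another table.

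What is at stake is safety, not inference. The appendix itself names cardiac arrhythmia as the hazard for pimozide, and prolonged sedation and respiratory depression as the hazards for the sedative group that includes zolpidem. With same-day screening and dosing allowed, the difference between the two pimozide entries can decide whether a participant is dosed that day or must wait.

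**Working it through.** There is no statistical figure to reproduce. The check sets the entries side by side and then looks for text that reconciles them.

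**Step 1. The entries.**

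| Drug | Entry A | Entry B | Difference |
|---|---|---|---|
| Pimozide | 24-hour list, Antipsychotics: stop 24 h or more before dose one | First-dose list, Neuroleptics: 0 h lead-in | 24 − 0 = 24 h |
| Zolpidem | First-dose list: any dose barred | Same block: barred above 5 mg daily | Up to 5 mg daily barred by A, not by B |
| Bosentan | Heading of its list: 0 h lead-in | Comment in its only row: 36 h before ritonavir | 36 − 0 = 36 h, heading against comment |

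Both pimozide entries end 4 days after the last dose, so they differ only before dosing.

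**Step 2. Is the pimozide duplication deliberate?** The 24-hour list has 22 entries: alfuzosin 1, analgesics 3, ranolazine 1, antiarrhythmics 5, colchicine 1, antipsychotics 3, ergots 3, statins 2, sildenafil 1, sedatives 2 (1 + 3 + 1 + 5 + 1 + 3 + 3 + 2 + 1 + 2 = 22). Pimozide is the only one of the 22 that reappears in the same form. Midazolam is split by route (oral in one list, parenteral in the other) and sildenafil by indication, so those are not conflicts. Nothing distinguishes the two pimozide rows except the class label.

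**Step 3. Does the zolpidem dose limit mean anything?** Elsewhere the same list uses daily dose limits to define what is barred: doxazosin above 2 mg, terazosin above 5 mg, amlodipine above 5 mg, atorvastatin above 20 mg, rosuvastatin above 10 mg, saxagliptin above 2.5 mg. Read the same way, the second zolpidem line leaves 5 mg or less outside the ban, and the first line bars it. Zolpidem is not in the precautionary table either, so that table does not settle the matter.

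**Step 4. Does other text settle which entry applies?**
- The introduction to Appendix 8 gives both start times and refers down to the tables. It does not say which applies to a drug listed in both.
- Exclusion 13 (Section 5.2) and Section 6.8 cover the dosing period and 4 days afterwards. Neither states a pre-dose stop for these drugs.
- The staff review of medicines before the first dose (Section 6.8) and the advice to consult the sponsor (Appendix 8) help only if the conflict is noticed.

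**Step 5. Can it matter in practice?** The Schedule of Activities says that screening can often be finished in under 24 hours. A participant still taking pimozide at screening and dosed the same day would meet the Neuroleptics row but not the Antipsychotics row. The 48-hour screening limit leaves room for a 24-hour or a 36-hour stop, provided that the site knows it must wait.

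**The case against.** The best reply is that these are overlapping prohibitions rather than contradictions. A ban from the first dose does not cancel one that starts 24 hours earlier, and barring more than 5 mg does not by itself license less. A site that obeys every entry complies fully, because the stricter condition satisfies both.

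The logic is right, but it does not rescue pimozide. The introduction to Appendix 8 describes the second tier as allowing use up to Day 1 before the first dose, so a site relying on that row would be following a stated rule. For zolpidem the reply is stronger, since both lines sit in one block and are easily seen together. They still give different answers at 5 mg or less.

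For bosentan much of the objection stands. A reader might infer that it carries two competing rules. The documents do not support that: the 36-hour instruction is in its only row, and anyone looking the drug up will read it as a drug-specific addition to the heading. It is a placement error.

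A reader might also infer that comments on monitoring or dose reduction in other rows, such as warfarin or digoxin, permit those drugs. They do not. The list heading makes a participant who cannot interrupt the drug ineligible, and Section 7.1 lists "Requirement for prohibited concomitant medication" among the reasons to stop study intervention permanently.

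The safeguards also count. Exclusion 13 can be read as excluding anyone currently taking such a drug, and qualified staff must review all medicines before dosing. These reduce the risk without choosing between the entries.

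**Conclusion.** The point holds as a minor safety-list inconsistency, wrong as written. Pimozide has two stop times that differ by 24 hours, zolpidem at 5 mg daily or less is both barred and not barred, and bosentan's 36-hour stop is under the wrong heading.

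The practical risk is limited. Pimozide is prohibited during dosing under either entry, so only the lead-in is in doubt. The documents do not say how many participants take these drugs, nor how much risk a shorter lead-in adds. That the number is small is an inference from Exclusion 1, which removes many people with chronic disease. The correction is useful only if participants are still being dosed. SAP Section 6.2.4 provides for participants enrolled under or after Amendment 6, which suggests that this was expected.

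A reader might infer that participants were harmed or that efficacy or safety results are compromised. Nothing in either document shows this. No endpoint, analysis set or statistical result depends on these entries.

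**What to change.** Use the written notification by which Appendix 8 already lets the sponsor revise the list, and make three edits:

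1. **Pimozide:** delete the Neuroleptics row from the first-dose list and keep the 24-hour entry.
2. **Zolpidem:** keep one entry, barred at any dose, unless the sponsor confirms that the limit of 5 mg daily was intended.
3. **Bosentan:** move it under a pre-dose heading that states its 36-hour stop.

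The cost is three table edits and one letter to sites. A general line saying that the stricter entry prevails is not recommended. Once the rows are corrected these three drugs do not need it, and it would need an immediate exception for ethinyl estradiol, which is in the prohibited list although Sections 6.8 and 10.4.4 allow estrogen-containing contraception with an added barrier method.

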10.9. Appendix 9: Signs and Symptoms Attributable to COVID-19

Table 2. Signs and Symptoms Attributable to COVID-19

Daily Sign and Symptom Collection ²⁹	Entry Criterion#3 Targeted (used for study entry)	Daily Signs and Symptom Collection	Targeted Symptoms For Analysis
Cough	X	X	X
Shortness of breath or difficulty breathing	X	X	X
Fever (documented temperature >38°C [100.4°F]) or subjective fever (eg, feeling feverish)	X		
Feeling feverish		X	X
Chills or shivering	X	X	X
Fatigue (low energy or tiredness)	X	X	
Muscle or body aches	X	X	X
Diarrhea (loose or watery stools)	X	X	X
Nausea (feeling like you wanted to throw up)	X	X	X
Vomiting (throw up)	X	X	X
Headache	X	X	X
Sore throat	X	X	X
Stuffy or runny nose	X	X	X
Loss of smell		X	
Loss of taste		X	

10.10. Appendix 10: Country-Specific Requirements

10.10.1. France

Contrat Unique

1. GCP Training

Before enrolling any participants, the investigator and any subinvestigators will complete the Pfizer-provided Good Clinical Practice training course (“Pfizer GCP Training”) or training deemed equivalent by Pfizer. Any investigators who later join the study will do the same before performing study-related duties. For studies of applicable duration, the investigator and subinvestigators will complete Pfizer GCP Training or equivalent every 3 years during the term of the study, or more often if there are significant changes to the ICH GCP guidelines or course materials.

2. Study Intervention

No participants or third-party payers will be charged for study intervention.

3. Urgent Safety Measures

In addition, the investigator will inform Pfizer immediately of any urgent safety measures taken by the investigator to protect the study participants against any immediate hazard, and of any serious breaches of this protocol or of ICH GCP that the investigator becomes aware of.

4. Termination Rights

Pfizer retains the right to discontinue development of PF-07321332 at any time.

10.10.2. Japan

A Protocol Administrative Change Letter was issued on 22 July 2021 to provide Japan country specific guidance regarding Exclusion Criterion #8.

Exclusion Criterion #8: Known HIV infection with viral load >400 copies/ml or taking prohibited medications for HIV treatment (from known medical history within past 6 months of the screening visit).

If HIV infection is known by medical interview or examination results (if any), the investigators must consult with the patient’s HIV treatment specialist to confirm that the HIV RNA level has been monitored at an appropriate frequency and the HIV RNA level has been ≤400 copies/mL during the past 6 months before the screening visit in order to assess the study eligibility of that patient.

Rationale: There is a risk for patients with uncontrolled HIV to develop resistance to ritonavir which is being administered with PF-07321332. According to the HIV treatment guideline in Japan, even if there is an occasional increase in the amount of HIV RNA in the blood to about 20-500 copies/mL, the same treatment may be continued. The guideline recommends a resistance test when HIV RNA levels exceed 500 copies/mL.

